This study (Figures 1 and 3) will include Option A consisting of 9 lab visits each approximately 2 hours long, except visit 1, which will last up to 3 hours **OR** Option B consisting of 5 lab visits each containing 2 vaping sessions separated by a 3-hour washout period and lasting approximately 6 hours. Figure 2 illustrates the study e-cig and e-liquid variations. Figure 3 depicts the sequence of the proposed study. We will conduct an experimental study examining how the manipulation of nicotine form (nicotine salt (NSB) vs. free-base (FB)) influences vaping behavior, abuse liability, toxicant exposure and heart and lung health.

Evaluating E-Cigarette Nicotine Form, Concentration, and Flavors among Youth

Figure 1. Vaping Session

Vaping Session	
12 hour nicotine abstinence	
Start of Session:	Surveys Respiratory Measures Cardiovascular Measures Blood Draw (0 min)
STD Puffing (5 min):	Blood Draw (5 min) Surveys
Ad-lib Puffing (30 min): Blood Draw (10 min) Blood Draw (35 min) Surveys	
3-hour washout (Visits 2-5 between vape sessions) (Option B Only)	
3 hrs. post exposure:	Respiratory Measures Cardiovascular Measures (Option B Only)
1 vaping session will occur at each visit for 9 visits (Option A Only)	
1 vaping session will occur at the first visit / 2 vaping sessions will occur at the final 4 visits (Option B Only)	

Figure 2. E-cig and e-liquid for Vaping Sessions

[figure not shown]
[figure not shown]

Figure 3. Study Sequence Option A and Option B

Evaluating E-Cigarette Nicotine Form, Concentration, and Flavors among Youth

ii. Study Procedures

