Utilizing a within-subjects, factorial design, 60 e-cig users (aged 21-25 years) will complete vaping sessions which will include a standardized, 5-minute, 10-puff vaping bout (30 seconds between each puff) followed by 30 minutes of ad libitum vaping. Prior to session one, participants will be asked to bring their own e-cig device and a full tank/pod to the first visit. In session one, participants will use their own e-cig and e-liquid. After visit 1, participants will take home a study e-cig device and 1 weighed pod pre-filled with study e-liquid (the participant was randomized to at the end of visit 1) to practice (20 puffs per day with the study device and until the participant feels comfortable) using the device before visit 2. Practice use with the study e-cig device and pre-filled pod will be verified based on data downloaded (via eScribe) from the device during visit 2. In the subsequent vape sessions, participants will use a study e-cig held at a constant wattage, and pre-filled with e-liquid of different nicotine form (free-base vs. nicotine salt), concentration (low-1% vs. high-5%), and flavoring (tobacco vs. menthol). There is no known commercial pair of nicotine liquids that differ only by nicotine form. For this study, we will prepare 8 e-liquids that differ by nicotine form, nicotine concentration, and flavor, simulating characteristics of popularly used nicotine liquids^{32,39}. E-liquids will be prepared from pure ($\geq 99\%$) S-(-)-nicotine; protonation and dilution of nicotine will be done using USP grade benzoic acid, and glycerol and propylene glycol, respectively. We will submit an Investigational Tobacco Product application to the U.S. FDA regarding the clinical use of the e-liquids. All sessions will be completed over nine visits for schedule Option A and 5 visits for schedule Option B. Study Schedule A consist of 9 separate visits and 9 separate vaping sessions. Study schedule B will consist of five separate visits (each visit will include up to 2 vaping sessions) each separated by a 3-hour washout period to allow nicotine levels to return to baseline. Each visit will be at least 48 hours apart. Participants will be required to report at least 12 hours abstinent from nicotine before each study visit. Participants will be told that their abstinence will be confirmed at the time of visit via blood plasma nicotine analysis. This is a partial bogus pipeline⁴⁰; 3mL venous blood sample will be collected for later analysis.; those with plasma nicotine levels $>3\text{ng/mL}$ at the time of their visit will be replaced post hoc with another participant. We conservatively estimate replacing 10% of participants. Measures of topography, nicotine uptake, abuse liability, subjective effects, and cardiovascular and pulmonary effects will be collected (see Table 1). Exposure to select toxicants, including nicotine and menthol in total particulate matter, and gas phase carbonyls and volatile organic compounds, will also be estimated post hoc using puff playback machine smoking.

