Laboratory Spirometry (SpiroLab)	X	X
Airway Inflammation (NIOX VERO)	X	X
Airway Reactivity (TremoFlo)	X	X
Cardiovascular Measures		
Vascular Reactivity (Vicorder or similar)	X	X
Blood Pressure	X	X
Heart Rate	X	X
Markers of endothelial dependent and independent function		
B-mode ultrasound (Vicorder or similar)	X	X
Arterial stiffness		
Pulse wave velocity and analysis (Vicorder or similar)	X	X

Evaluating E-Cigarette Nicotine Form, Concentration, and Flavors among Youth

E. Statistical Methods

Generalized linear mixed models will be employed to identify associations of nicotine form, nicotine concentration, and flavoring with various outcome measures (e.g., plasma nicotine, spirometry, flow-mediated dilation). Models will include relevant covariates (e.g., gender), a random effect for participant, main effects for nicotine form and concentration, and the interaction between nicotine form and concentration and nicotine form and flavor. Because of multiple measurements tested, we will assume a significance threshold corresponding to one expected false discovery per 100 tests ($p=0.01$).

i. Power Analysis

This study, for each of the main effects and $\alpha = 0.01$, achieves 80% power to detect an effect size of 0.5 standard deviations of the paired differences. For interaction effects, we will estimate 80% power (effect size 0.5 SD) to distinguish between any two of the interaction groups (e.g., free base/low nic, free base/high nic), while correcting for the pairwise tests ($p=0.01/6=0.0017$). Carryover and period effects will also be examined.

ii. Data Analytic Plan

Because product sampling will be randomized using a Latin Square, a fixed effect for session and a random effect for sequence will be included in all analyses.

iii. Missing Data

While we will make every effort to minimize the missing data for this study, missing data can arise due to various reasons. Violation of missing complete at random (MCAR) will be checked by evaluating whether any covariates are associated with missing data. If so, these covariates will be subsequently included and controlled for in the GLMM model. Our primary analysis will use mixed models which assumes Missing At Random (MAR) to deal with the missing data problem. In addition, sensitivity analyses will also be conducted using results from multiple imputation and complete cases strategies.

F. Gender/Minority/Pediatric Inclusion for Research

i. Inclusion of Women and Minorities

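### Replacing a whole participant for a visit-level abstinence failure gives up six to eight valid randomized sessions that the planned mixed model could keep

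*Combined protocol and SAP*

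**What the plan says.** Section D.ii sets the condition for every visit: "Participants will be required to report at least 12 hours abstinent from nicotine before each study visit". The biochemical check is not a same-day result: "3mL venous blood sample will be collected for later analysis". Those above 3 ng/mL when they attend "will be replaced post hoc with another participant". The expected size is given without a derivation: "We conservatively estimate replacing 10% of participants".

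The number of checks depends on the schedule, which participants choose (section D.ii.1, Retention and Compensation). For Option A, "Study Schedule A consist of 9 separate visits and 9 separate vaping sessions". For Option B, Figure 1 says "1 vaping session will occur at the first visit / 2 vaping sessions will occur at the final 4 visits (Option B Only". The first session uses the participant's own device and liquid; the other eight use the eight study liquids. Randomization is at the end of visit 1.

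Section E.ii allocates products by Latin square, with session as a fixed effect and sequence as a random effect. Section E.iii says "Our primary analysis will use mixed models which assumes Missing At Random (MAR) to deal with the missing data problem", with multiple-imputation and complete-case sensitivity analyses.

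Section E defines no analysis set and does not mention the replacement rule. The document does not state how many failing visits trigger replacement, when the assays are run, whether a replaced participant's data are deleted, or whether the new participant takes over the same sequence.

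**The concern.** A raised value at one visit casts doubt on that visit's sessions. It says nothing against the same person's sessions on other days, which start from their own abstinence check. In a within-person design those other sessions carry direct information on the product contrasts, and a mixed model uses them without needing a complete set of eight. A rule that removes the person gives up that information and requires someone else to be run through the whole schedule.

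Three further consequences follow. The chance of removal grows with the number of checks, so it can differ between the two schedules. Most triggering samples would be taken after randomization. And removal is triggered by failed abstinence in a study of abuse liability, so the analysed sample is narrowed on a characteristic close to the research question.

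**Working it through.** **Inputs.** Section D.ii: 60 analysed participants, 10% replaced, 8 randomized sessions each. Section D.ii and Figure 1: 9 visits (Option A), or 5 visits with 1 + 4 × 2 = 9 sessions (Option B). Section E.i: alpha 0.01, effect 0.5 SD of paired differences, 80% power.

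**1. The plan's own figures.** At 10% replacement, 60 / (1 − 0.10) = 66.7, so 67 are run and 7 replaced. For power, a two-sided paired t-test with n = 60, 0.5 SD and alpha 0.01 gives 88% (90% by normal approximation). The stated 80% for main effects is therefore conservative, and because the rule restores 60 it does not lower this figure.

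**2. Valid randomized sessions lost per replaced person, one failing visit.**
- Option A, one randomized visit fails: 8 − 1 = 7.
- Option B, one randomized visit fails: 8 − 2 = 6.
- Either option, only visit 1 fails: 8 − 0 = 8. The failing sample then comes from the own-device session, before randomization.

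**3. Across the trial at 10%.** The 67 participants give 67 × 8 = 536 randomized sessions. The participant-level rule keeps 60 × 8 = 480.

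| Each of the 7 fails | Valid sessions dropped now | Kept under a visit-level rule |
|---|---|---|
| one randomized Option A visit | 7 × 7 = 49 | 536 − 7 = 529 |
| one randomized Option B visit | 7 × 6 = 42 | 536 − 14 = 522 |
| visit 1 only | 7 × 8 = 56 | 536 |

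If only 60 were enrolled and nobody added, 10% failing is 6 people. With one randomized visit failing each, a visit-level rule would leave 480 − 6 = 474 sessions (A) or 480 − 12 = 468 (B).

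**4. Number of checks.** Assume a per-visit failure rate q, the same for everyone and independent across visits. The chance of at least one failure is 1 − (1 − q)^k, with k = 9 (A) or 5 (B). The documents give no per-visit rate, so the values of q below are assumptions.

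| q | Option A removed | Option B removed | Randomized sessions lost if only failing visits are dropped |
|---|---|---|---|
| 2% | 17% | 10% | 2% |
| 3% | 24% | 14% | 3% |
| 5% | 37% | 23% | 5% |

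Working backwards, 10% of participants corresponds to q = 1 − 0.9^(1/9) = 1.2% under A and 1 − 0.9^(1/5) = 2.1% under B.

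**5. Before or after randomization.** Under the same assumption and the planned 10%, the share of removals in which visit 1 is the only failure is q(1 − q)^(k−1) / 0.10, which is 11% (A) or 19% (B). The other 89% or 81% involve a failing visit after randomization. The average loss per replaced person, [8(1 − q) − 8(1 − q)^k] / 0.10, is 7.1 valid randomized sessions (A) or 6.3 (B).

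**6. If failures cluster within people.** Someone who fails m randomized visits loses 8 − m valid sessions (A) or 8 − 2m (B), so repeat failers have less to discard. For a given q, fewer people are removed than in the table, and the gap between the options narrows.

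**The case against.** Much of the opposing case stands. The single-visit trigger, removal only after the schedule is finished, and deletion of the data are readings of the rule, not statements in it. Visits are at least 48 hours apart, so assays during follow-up are not ruled out. The eight-session loss needs visit 1 to be the sole failure, which is close to a late screening failure.

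A reader might infer a large loss of power. At 5% per visit with everyone on Option A, 60 × 0.95^9 is about 38, and power would fall from 88% to 64%. But that requires no replacement, and the rule is a replacement rule. Even without replacement, the planned 10% leaves 54 participants and 84% power.

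A reader might also infer that recruitment would fail. Section D.ii.1 recruits 130 with 20% attrition: 130 × 0.8 = 104, and 104 × 0.95^9 is about 66, still above 60. The text does not tie the 130 to this rule, and 60 / 0.8 = 75 or 60 / (0.8 × 0.9) = 84 does not reproduce it; its origin is a separate question.

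A reader might infer a contradiction with the missing-at-random strategy. There is none: a plan can replace people who fail an entry condition and also model missing sessions. The two are simply not linked.

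Finally, a reader might infer biased product contrasts. The eligibility criteria already require willingness to abstain for 12 hours, and the contrasts are within person. Bias would need product effects that vary with dependence, or failures that depend on earlier products, and the documents give no data on either. That the most dependent users fail most often is plausible but also undocumented.

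None of this gives a reason to drop valid sessions from other days, and the plan offers none.

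**Conclusion.** The concern holds in a limited form and is worth correcting. The plan attaches a person-level consequence to a visit-level failure and has no provision for keeping the valid remainder. At its own 10%, with one failing visit per replaced person, that costs about 42 to 56 valid randomized sessions out of 536. The range rests on reading replacement as triggered by one visit and as removing all of the person's data.

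The schedule difference (for example 17% against 10% removed at an assumed 2% per visit) rests on equal and independent failure rates, and clustering would shrink it. That most triggering samples would follow randomization rests on the same assumption. Nominal power at 60 is intact. The costs are forgone precision, replacement recruitment, possible Latin-square imbalance because sequence reassignment is undefined, and a sample further selected on ability to abstain, which mainly limits generalizability.

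**What to change.** Make the rule visit-level, in section D.ii and section E:

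- Keep every randomized participant in the primary mixed model. Set to missing only the session or sessions of a visit whose visit-start plasma nicotine exceeds 3 ng/mL. If only visit 1 fails, only the own-device session is affected.
- Define visit-start as the sample before the first session of the day. In Option B, the value before the second session can carry over from the product vaped earlier that day, so it should serve neither as the criterion nor as a covariate.
- As a sensitivity analysis, include all sessions and adjust for the visit-start value. This should not be the primary analysis: it keeps non-abstinent sessions, and adjusting for plasma level need not restore the abstinent state that the craving and withdrawal measures presuppose.
- Added participants may still be enrolled to reach 60, but the valid sessions of those they supplement stay in the model. State how added participants are assigned a sequence.
- State when assays are run, report failing visits by schedule, and include visit 1 dependence among the covariates checked against missingness under section E.iii.

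The cost is protocol and SAP wording and one further model run, with less replacement recruitment. Some participants will contribute fewer than eight sessions, which the planned model handles under its missing-at-random assumption.

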Lastly, the tobacco industry, especially in the manufacturing of smokeless tobacco products, manipulated pH to develop “starter products”—the industry’s term for products that are highly flavored, with a combination of low pH and low nicotine¹⁹. These products were developed to facilitate tobacco product initiation and to increase uptake and addiction¹⁹. Over time, as users developed tolerance to nicotine, they were able tolerate products with higher levels of biologically available nicotine¹⁹. While JUUL, the e-cig market leader with approximately 50% of unit sales and nearly 80% of the estimated market dollar share³⁶, originally only contained e-liquid with a nicotine concentration of 5%, the company now offers a lower nicotine concentration pod (3% nicotine), which is strangely higher than 20 mg/mL permitted for e-liquids sold in the European Union³⁶. JUUL has provided no rationale for the lower nicotine concentration pod. Given that the 5% nicotine pod has demonstrated nicotine delivery and subjective effects that almost completely mimic a combustible cigarette³⁶, the potential for compensation (i.e., greater consumption rate for the 3% nicotine pod) is high. Additionally, it is likely that with reduced nicotine concentration, these devices will be even more palatable, especially to nicotine naïve users. In summary, controlled studies examining the interaction between e-liquid pH and nicotine concentration are critical to help public health officials determine how manipulation of these levels influence users’ device power settings, subjective effects and puffing topography, as they are critical in the determination of abuse liability and exposure to harmful tobacco toxicants and disease risk.

C. Approach and Preliminary Studies

Our team has conducted five studies examining NSB e-cig devices¹¹⁻¹³, including two recently completed human laboratory studies^{11, 12}. Results of these studies demonstrated that NSB e-cigs can deliver cigarette-like levels of nicotine^{28, 38}, have the potential for significant levels of addiction¹¹⁻¹³, and that lower e-liquid pH was associated with reduced perceived harshness of the aerosol ($p < .05$), increased nicotine uptake ($p < .05$), and increased puffing flow rates and average puff volumes ($ps < .05$).

D. Research Design and Methods

i. Design Overview

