
1. Recruitment Feasibility and Retention

a) Recruitment

We intend to recruit 130 e-cig users from the community over an 18-month period and have them complete nine study visits (Option A) or five study visits (Option B); therefore, we need 3-4 participants to be recruited and complete study procedures per month.

We are confident our recruitment approach, laboratory facilities, and equipment redundancy will result in a sufficient participant processing rate, given our successful completion of other tobacco-related research of similar design⁴¹. E-cig users will be recruited from advertisements through a variety of media outlets and the internet, including Study Search, as well as community events. Participants from

Evaluating E-Cigarette Nicotine Form, Concentration, and Flavors among Youth

other studies who have agreed to be contacted regarding other study opportunities will also be contacted. Staff from those studies will prepare contact letters/emails and call participants on behalf of this study. Interested participants will be referred to this study for screening. Participants will access the screening questionnaire using a public survey link generated by REDCap. Based on our team's previous studies, we conservatively assume a 20% attrition rate. Thus, we need to recruit 130 participants to have 60 complete the study. Participants who meet the following eligibility criteria will be asked to take part in the study.

Inclusion criteria: 1) a current e-cigarette user (≥ 1 vaping bout per day) for at least the past 3 months , 2) 21-25 years old, 3) willing to abstain from all tobacco and nicotine for at least 12 hours prior to lab sessions, 4) willing to complete nine lab visits/vaping session lasting up to 2 hours each or five lab visits lasting up to 6 hours each (except Visit 1) , 5) able to read and speak English, 6) willing to provide informed consent

Exclusion criteria: 1) self-reported diagnosis of lung disease including asthma, cystic fibrosis, or chronic obstructive pulmonary disease, 2) history of cardiac event or distress within the past 3 months, 3) currently pregnant (determined using urine pregnancy test), planning to become pregnant, or breastfeeding, 4) use of other tobacco products >10 days in the past month, 5) current marijuana use >10 times per month, 6) currently engaging in a vaping cessation attempt.

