Participants' eligibility will be determined over the phone or via REDCap's online screener. Those who are eligible and willing to participate will be invited to sign an informed consent and complete their baseline visit in a private participant room at the Ohio State University. All participants will be given adequate time to review the informed consent with a trained research staff to help answer any questions that may arise during the consent process. Additionally, a copy of the informed consent will be given to all participants. A pregnancy test will be completed at the initial visit as well as before starting all the in-lab visits to ensure that the participant is not pregnant.

b) Retention and Compensation

If participants choose Option A, they will receive \$50, \$50, \$50, \$50, \$75, \$75, \$75, \$75, and \$100 for completing visit 1, 2, 3, 4, 5, 6, 7, 8, and 9, respectively, for a total of \$600. Participants who choose Option B will receive \$50, \$100, \$125, \$150, and \$175 for completing visit 1, 2, 3, 4 and 5, respectively, for a total of \$600. Consistent with our previous studies, payments will be made using the Greenphire ClinCard to increase accountability and facilitate ease of payment. We will facilitate visits by offering weekend appointments and using additional retention strategies (e.g., reminder calls/texts/emails). Participants will receive reminder calls in addition to email or text reminders. Reminders will be sent by text or email based on a participant's preferred method of contact.

2. Detailed Study Procedures

a) Study Sessions

Prior to the start of the first laboratory visit, twelve-hour tobacco abstinence will be assessed via self-report and confirmed with exhaled carbon monoxide testing ($eCO \leq 10$ ppm). A research assistant will

Evaluating E-Cigarette Nicotine Form, Concentration, and Flavors among Youth

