There are minimal risks associated with this protocol. The protocol requires e-cig users 21 to 25 years of age to undergo 12 hours of tobacco/nicotine abstinence on nine occasions. These e-cig users will complete 9 vaping sessions – one session in which participants will use their own e-cig and e-liquid and subsequent sessions in which participants will use a study e-cig held at a constant wattage, and pre-filled with e-liquid of different nicotine form (free-base vs. nicotine salt), concentration (low-1% vs. high-5%), and flavoring (tobacco vs. menthol).

The participants are already using e-cigarettes and will only be asked to use or switch to what will be a fully characterized e-cigarette device and ITPs that have been fully described to FDA Center for tobacco products. Questionnaires, exhaled breath, and urine collection procedures are all non-invasive and involve minimal risk to study participants. Potential risks are as follows: a) risk of using e-cigarettes, b) loss of confidentiality or privacy, and c) risk of infection from blood draws.

1. Risk of Using ECs:

Risks

The risk of side effects and adverse events are very low. The commercial device we are using is sold online, and at e-cigarette specialty stores and convenience stores nationwide, without a prescription.

Protections

Evaluating E-Cigarette Nicotine Form, Concentration, and Flavors among Youth

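### Inclusion criterion 1 requires daily vaping but not nicotine-containing e-liquid, so eligibility does not secure the assumption that participants already use nicotine

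*Combined protocol and SAP*

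**What the plan says.** Section D.ii.1.a (Recruitment) sets the first inclusion criterion as "a current e-cigarette user (≥ 1 vaping bout per day) for at least the past 3 months". The third asks that the person be "willing to abstain from all tobacco and nicotine for at least 12 hours prior to lab sessions". Neither these nor the remaining inclusion and exclusion criteria ask about the nicotine content of the usual e-liquid.

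Abstinence is checked by self-report and exhaled carbon monoxide of 10 ppm or less at the first visit (D.ii.2.a). Plasma nicotine is analysed later, and anyone above 3 ng/mL at a visit "will be replaced post hoc with another participant" (D.ii). The plan adds: "We conservatively estimate replacing 10% of participants".

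The study liquids cross nicotine form, concentration (1% or 5%) and flavour. After visit 1 each participant takes home a study device and a filled pod to practise with at 20 puffs per day (D.ii, D.ii.2.a, D.ii.2.b).

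The risk section (G.ii) states: "The participants are already using e-cigarettes and will only be asked to use or switch to what will be a fully characterized e-cigarette device". It also counts nine occasions of 12-hour tobacco or nicotine abstinence.

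**The concern.** The design treats participants as nicotine users. It asks them to abstain from nicotine, measures craving and withdrawal as an abuse-liability domain, and rests its low-risk argument on people using or switching to a characterized product. The eligibility rules ask only for vaping. For a person whose usual liquid has no nicotine, the study liquids may be a start of nicotine use rather than a switch.

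Two things are at stake. First, the protocol's risk argument, including the expectation in G.ii.1 that nicotine-related events will be rare (under 5%, from the team's earlier studies), may not carry over to such a person. The first exposure to study liquid would be at home. Second, 12 hours without nicotine may produce little withdrawal in someone who does not normally take it, so there may be little craving to suppress. Their responses to concentration and form may also differ from those of regular nicotine users.

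**Working it through.** **1. Does any rule exclude a nicotine-free daily vaper?**
- Inclusion criterion 1: met, because it counts vaping bouts only.
- Inclusion criterion 3: met, because willingness to abstain does not require prior use.
- Other inclusion criteria (age, visits, English, consent): no bearing on nicotine.
- Exclusions (lung disease, cardiac event, pregnancy, other tobacco, marijuana, cessation attempt): none requires nicotine use.
- Self-report, exhaled CO and plasma nicotine: upper limits only. No minimum level or rise is required.

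As written, the person is eligible.

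**2. What would the person receive?** 2 forms × 2 concentrations × 2 flavours = 8 liquids. All contain nicotine and 8/2 = 4 are at 5%. There is no 0% liquid. The take-home pod therefore also contains nicotine.

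**3. Would the plan notice?** Visit 1 collects tobacco use history, Timeline Followback, e-cigarette dependence, the nicotine concentration of the e-liquid (Table 1) and plasma nicotine at four time points on the person's own product. No rule links any of these to eligibility or to release of the pod. Section E names gender as an example covariate and a random effect for participant; it does not name usual nicotine strength.

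**4. How many people?** The documents give no share, so this range is an assumption. At 2%, 60 × 0.02 = 1.2; at 10%, 60 × 0.10 = 6. Each would contribute 8 study-liquid sessions. If craving suppression were zero in them, the mean would shrink by the same 2% to 10%.

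**5. Does the replacement rule shift the mix?** Suppose 10% of nicotine users and no nicotine-free vapers are replaced. An enrolled share of 10% then becomes 0.10 / (0.10 + 0.90 × 0.90) = 0.10 / 0.91 = 11%. This is an upper bound for that starting share, because nicotine-free vapers can be replaced too (see the objection).

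**6. What could it do to power?** The plan states 80% power for 0.5 SD of paired differences, at alpha 0.01 for main effects and 0.01/6 = 0.0017 for interaction pairs. With n = 60, 0.5 × √60 = 3.873. A two-sided paired t test gives 88% and 71%; the normal approximation gives 90% and 77%. Neither reproduces 80% for both, which is a separate matter. The t figures serve as the baseline.

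Let a share f respond with k times the 0.5 SD effect, with within-class SD 1. The standardized effect is d = 0.5(1 − f + fk) / √(1 + f(1 − f)(0.5 − 0.5k)²). For example, f = 10% and k = 0 gives 0.45 / √1.0225 = 0.445.

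| Assumed f | Assumed response in nicotine-free vapers | d | Main effect | Interaction pair |
|---|---|---|---|---|
| 0 | none enrolled | 0.50 | 88% | 71% |
| 5% | no effect (k = 0) | 0.47 | 84% | 64% |
| 10% | no effect (k = 0) | 0.45 | 78% | 56% |
| 10% | reversed (k = −1) | 0.38 | 62% | 38% |
| 10% | doubled (k = 2) | 0.54 | 94% | 81% |

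The sign of the change depends on k, which the documents do not supply.

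**The case against.** The best defence is that the intended population is evident. Nicotine abstinence is required throughout, and the exclusion on other tobacco products treats the e-cigarette itself as one. The screener questions are not shown and may already ask about nicotine. Visit 1 data would identify a nicotine-free vaper, and the covariate list is open-ended. The comparison is within person, so differences in level between people drop out. All of this stands, but none of it is an eligibility rule, and the participant effect does not remove differences in response.

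A reader might infer more than the documents support:
- **That the risk section is contradicted.** It says participants already use e-cigarettes, which a nicotine-free vaper does. What goes unsecured is the implied premise of existing nicotine use.
- **That such a person passes every check and can never be replaced.** Other tobacco use is allowed on up to 10 days in a month, and the practice pod contains nicotine, so CO or plasma nicotine can exceed the limits.
- **That H1c is inflated or the results are distorted.** H1c compares free-base with salt at high concentration. Unaccustomed users might find only the free-base liquid aversive, or both; the contrast could grow or shrink.
- **That the plan says tolerance decides who can use the study liquids.** The sentence "Over time, as users developed tolerance to nicotine, they were able tolerate products with higher levels of biologically available nicotine" (section B.2) describes starter products, chiefly smokeless tobacco. Section B.2 also treats nicotine form as affecting palatability.

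**Conclusion.** The gap is real: as written, eligibility admits daily vapers who do not use nicotine, and nothing later in the plan screens them out for that reason. The eligibility and risk point does not depend on prevalence, since one such participant is enough. For the analysis, the conclusion is only that the craving-suppression, concentration and form contrasts could be diluted or otherwise altered. The 2% to 10% share and the response patterns in the power table are assumptions, and the share, direction and size of the effect cannot be determined from the documents. The enrichment through replacement is at most about one percentage point at an assumed 10% share. This is a cheap improvement to the eligibility wording. It does not show that the planned comparisons are invalid.

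**What to change.** Reword criterion 1 to require a current user of nicotine-containing e-cigarettes, with at least one bout per day of nicotine-containing e-liquid over the preceding 3 months. Add the matching question to the REDCap screener. Confirm it at visit 1 from the label of the pod or tank the participant already brings, or by self-report if it is self-filled, before randomization and before the practice pod is issued.

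The cost is one phrase, one question and a brief check. The few nicotine-free vapers can no longer be recruited. The change sets no minimum strength, so users of weak liquids still qualify, and self-report for a self-filled tank is weaker evidence than a label.
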